# **Background**

The Jockey Club Holistic Support Project for Elderly Mental Wellness (JC JoyAge) has developed and implemented a collaborative stepped care model for older persons atrisk of or with depression in four districts in Hong Kong since 2015 (Clinical Trials Identifier: NCT03593889). Results from JC JoyAge show that the collaborative stepped-care model is effective in improving older persons' mental wellness, and the specialised training and engagement of Peer Supporters are effective in building capacity in the community. The proposed impact extension programme will be four years (from 2020 to 2023), and the overall goal is to expand the JC JoyAge model to all 18 districts in Hong Kong, to provide integrated and evidence based mental health services to older adults with subclinical depressive symptoms, with the hope of model adoption in regular service upon project completion.

# **Objectives**

- a) To implement JC JoyAge clinical protocol and guidelines to coordinate care among community mental health and elderly services centres for elderly mental wellness in 18 districts;
- b) To engage vulnerable and at-risk older adults in the community through productive ageing activities and mental wellbeing self-management training;
- c) To enhance the capacity of social service staff in handling elderly depression through specialized and *infusion* training and knowledge exchange;
- d) To raise public awareness and elderly mental health literacy among family members, neighbours, community stakeholders, and the general public to encourage early detection/help-seeking on depressive risk of older adults; and
- e) To establish evidence of the effectiveness and cost-effectiveness of JC JoyAge Phase II model.

# Methods

#### Design

This intervention study is designed as a prospective, open-labelled, single-arm trial. In the one-group pretest-posttest design, data will be collected at the baseline (T0), after completion of the intervention (T1), and after completion of the exit-plan (T2).

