## **Participants**

Older people with mild to moderately severe depressive symptoms (n=3,000) recruited from 14 JoyAge partner non-governmental organisations (NGOs) in 18 districts in Hong Kong.

The inclusion criteria for participants are:

- age 60 years or above; and
- have depressive symptoms of mild level or above; and
- able to give informed consent to participate

The exclusion criteria for participants are:

- known history of autism, intellectual disability, schizophrenia-spectrum disorder, bipolar disorder, Parkinson's disease, or dementia; and
- (temporary exclusion criteria) imminent suicidal risk; and
- difficulty in communication

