### **Assessment Procedures**

After basic screening, baseline evaluation (T0/intake) will be performed by trained social worker employed by NGOs and clinical information will be used for triage. After completion of the intervention or drop-out, a progress review evaluation (T1/review) will be done by social worker as well, and a client is discharged if he/she meets the exit criteria at T1. For dischargeable client, a 2-month exit plan will be provided, and he/she will be assessed at the end of the exit period (T2/exit) by Peer Supporters, specifically on progress in personal goals of recovery.

Assessment will last for around 60 minutes for all participants at T0 and T1, and for around 30 minutes at T2 for those who are eligible for discharge.

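### Objective (e) seeks evidence of effectiveness and cost-effectiveness, but the plan compares one open-label group only with itself over time and does not limit the claim; eight outcomes are primary with no lead outcome

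*Combined protocol and SAP*

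**What the plan says.** Objective (e) is "To establish evidence of the effectiveness and cost-effectiveness of JC JoyAge Phase II model", and the Background section looks ahead to use of the results, "with the hope of model adoption in regular service upon project completion". The Design section says "This intervention study is designed as a prospective, open-labelled, single-arm trial", in which "data will be collected at the baseline (T0), after completion of the intervention (T1), and after completion of the exit-plan (T2").

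Under Participants, 3,000 older people are to come from 14 NGOs. One entry condition is to "have depressive symptoms of mild level or above".

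Under Assessment Procedures, "After basic screening, baseline evaluation (T0/intake) will be performed by trained social worker". Then "After completion of the intervention or drop-out, a progress review evaluation (T1/review) will be done by social worker as well". T2 is done by Peer Supporters, and its length is given as "for around 30 minutes at T2 for those who are eligible for discharge".

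Measurements numbers eight primary outcomes:
1. PHQ-9
2. GAD-7
3. UCLA-3
4. Self-harm risk
5. EQ-5D-5L
6. Five RAS items
7. A recovery-goal questionnaire
8. Health care expenditures (CSRI)

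The same section confines measurement at T2 to the primary outcomes.

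Data Analysis applies repeated measures and growth curve models to three main domains: depressive symptoms or risks, wellbeing, and personal recovery. It promises effect sizes, significance and confidence intervals. It also plans a cost-utility analysis reported as an incremental ratio per QALY.

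**The concern.** Effectiveness is a causal claim: it concerns what happened relative to what would have happened without the programme. The planned models estimate only what happened. Effect sizes and confidence intervals do not help, because they describe the same within-person change. T2 is not a control either, since it is taken only in people eligible for discharge at T1. An incremental cost-utility ratio likewise needs something to be incremental to, and none is named.

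The sample is large enough for a small natural fall to be statistically significant. Such a result could be reported as meeting objective (e) and used to support adoption in regular service. With eight unranked primary outcomes, the reader also cannot tell which result is meant to carry the conclusion.

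**Working it through.** **1. Is there a comparator?** Objective (e) promises effectiveness and cost-effectiveness. Design gives one group and three time points. Data Analysis models change over those points. Interventions speaks of an intervention group, but no other group exists. Background cites the earlier JoyAge work without planning to use it as a control. NGO social workers do T0 and T1, and registered social workers employed by the NGOs deliver the interventions, all open label. No sentence restricts what may be concluded.

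**2. How small a natural fall would be significant?** The documents give no alpha, power, SD or derivation of 3,000, so there is no planned figure to reproduce. Assumptions: two-sided 5%, 80% power, no programme effect, PHQ-9 change SD 2.7 to 6.0, and all 3,000 seen at T1.

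- No clustering: (1.96 + 0.842) × SD / √3000. This gives 0.138 at SD 2.7 and 0.307 at SD 6.0.
- Clustering by NGO, equal sizes assumed: 3000/14 = 214.3 per NGO, and the design effect (DE) is 1 + 213.3 × ICC. ICC 0.01 gives 3.13 and ICC 0.05 gives 11.66. With 13 degrees of freedom the critical t is 2.16, and 80% power needs a noncentrality of about 3.03. The fall is 3.03 × SD × √(DE/3000).

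| Seen at T1 | No clustering | ICC 0.01 | ICC 0.05 |
|---|---|---|---|
| 3,000 | 0.14–0.31 | 0.26–0.59 | 0.51–1.13 |
| 1,500 | 0.20–0.43 | 0.30–0.67 | 0.53–1.18 |

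Entries are PHQ-9 points for SD 2.7 to 6.0. The second row uses 1500/14 = 107.1 per NGO and design effects of 2.06 and 6.31.

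**3. Does regression to the mean add to this?** That depends on which reading decides entry, which is not stated, because basic screening precedes T0. The simulation assumed no programme effect, source mean 3, 6 or 9, between-person SD 3.5, within-person SD 2.0–3.0, and entry scores 5–19. With independent fluctuations between occasions, the T0–T1 fall is:

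- T0 alone decides: about 0.2–1.9 points.
- Screening and T0 must both qualify: about 0.2–1.4.
- Screening alone decides: about zero.

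The last result depends on independence. If fluctuations correlate 0.5 between screening and T0 and 0.1 between T0 and T1, screening-only entry gives about 0.1–0.8 points. At 0.8 and 0.3 it gives about 0.1–1.0. Under screening-only entry with independent fluctuations, the screening-to-T0 change itself contains 0.23–1.87 points of regression to the mean.

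**4. Which outcomes are analysed?** On a plausible mapping, PHQ-9 and self-harm risk belong to depressive symptoms or risks, EQ-5D-5L to wellbeing, and RAS and the recovery-goal questionnaire to personal recovery. That places five of the eight. CSRI goes to the cost-utility analysis. GAD-7 and UCLA-3 are named in no analysis.

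Family-wise error, if each test used an assumed 5% and every true change were zero:

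- Three tests: 1 − 0.95³ = 14% if independent, 11–14% at correlations 0.7 to 0.3.
- Five tests: 1 − 0.95⁵ = 23% if independent, 15–21% at the same correlations.
- Eight independent tests: 1 − 0.95⁸ = 34%.

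**The case against.** The design is openly declared as single-arm and may suit a service roll-out. Four of the five objectives concern implementation, engagement, training and awareness. Background says earlier JoyAge results already show the model to be effective. Data Analysis sets no rule that a significant result means success. All this is true, and it is why no control arm is demanded here. It does not close the gap, because objective (e) promises evidence on the Phase II model and this study supplies only within-person change.

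Four stronger readings are tempting and should be resisted.

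- *Regression to the mean must inflate the result.* The documents do not say which reading decides entry or how scores fluctuate over time. Its size could be near zero or above a point.
- *The false-positive risk is 34%.* That needs eight independent tests and a rule that any one suffices, which the plan does not state. It also assumes no true change in any outcome, which sits badly with the argument that natural change is likely. The real gap is the missing hierarchy.
- *The outcome list and the analysis do not match.* Most of the list has a place. Only anxiety and loneliness do not.
- *PHQ-9 is implicitly the lead outcome.* It is listed first, and the goals of all three intervention levels are stated as depressive symptom level. But numbering is not declared a ranking, and no time point is singled out.

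**Conclusion.** The point holds. As written, the plan cannot deliver objective (e): natural recovery, possible regression to the mean and unblinded assessment all remain inside the estimated change, and inside any cost-utility ratio built on it. This conclusion rests on the text and needs no assumed number.

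The size is illustrative. A natural fall of about one PHQ-9 point or less would probably be significant with an inert programme over nearly all of the assumed range. The exception is an SD near 6.0 with within-NGO correlation 0.05, where 1.13–1.18 points are needed. How far scores would actually fall without the programme is unknown from the documents, so a reader should not infer that a false claim is certain.

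The missing lead outcome, time point and multiplicity rule are a real but lesser defect. On their own they would be a matter of clarity.

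**What to change.** 1. **Limit the claim.** Reword objective (e) to describing uncontrolled before-after change in outcomes, costs and QALYs. Add to Data Analysis: *A significant change from T0, or a cost-utility ratio built on it, will not by itself be taken as evidence of effectiveness or cost-effectiveness, because natural recovery, regression to the mean and unblinded assessment are not separated from programme effect.* State the comparator for the incremental ratio, or report it as a before-after ratio.

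2. **Name a lead outcome, in this order.** First replace the Measurements sentence that ties T2 measurement to primary status with an explicit list of T2 measures. Otherwise demoting an outcome would remove T2 data that the three-time-point models and the sustained cost-effectiveness analysis need. Then name one lead outcome and time point, for example PHQ-9 change from T0 to T1 in all enrolled. T1 suits this because it is planned after completion or drop-out, whereas T2 is limited to those eligible for discharge. Make the rest secondary, or state a multiplicity adjustment if several stay primary. Give GAD-7 and UCLA-3 a place in the analysis.

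3. **Optional.** State which reading decides eligibility. If screening PHQ-9 scores exist and are reported, warn that the screening-to-T0 change may itself contain regression to the mean and is not an estimate of natural recovery.

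The cost is protocol and SAP wording, with no new data. The claim becomes more modest and fewer outcomes carry primary status.

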## **Participants**

Older people with mild to moderately severe depressive symptoms (n=3,000) recruited from 14 JoyAge partner non-governmental organisations (NGOs) in 18 districts in Hong Kong.

The inclusion criteria for participants are:

- age 60 years or above; and
- have depressive symptoms of mild level or above; and
- able to give informed consent to participate

The exclusion criteria for participants are:

- known history of autism, intellectual disability, schizophrenia-spectrum disorder, bipolar disorder, Parkinson's disease, or dementia; and
- (temporary exclusion criteria) imminent suicidal risk; and
- difficulty in communication

### **Assessment Procedures**

After basic screening, baseline evaluation (T0/intake) will be performed by trained social worker employed by NGOs and clinical information will be used for triage. After completion of the intervention or drop-out, a progress review evaluation (T1/review) will be done by social worker as well, and a client is discharged if he/she meets the exit criteria at T1. For dischargeable client, a 2-month exit plan will be provided, and he/she will be assessed at the end of the exit period (T2/exit) by Peer Supporters, specifically on progress in personal goals of recovery.

Assessment will last for around 60 minutes for all participants at T0 and T1, and for around 30 minutes at T2 for those who are eligible for discharge.

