## **Interventions**

Participants in the intervention group will receive a collaborative stepped care programme provided by registered social workers and trained Peer Supporters from elderly service units, the Districts Elderly Community Centres (DECC), and mental

health service units, the Integrated Community Centre on Mental Wellness (ICCMW), all local NGOs. In the collaborative stepped care model (see Table 1), older persons are matched to the intervention module that most suits their current needs. The person does not have to start at the lowest level of intervention to progress to the next level of intervention. Rather, they enter the service with the intervention level aligned to their needs, e.g., level of risks, symptom severity (measured by the Patient Health Questionnaire, PHQ-9), and intervention response. Home visits or other format of contact will be delivered by trained Peer supporters employed by the NGOs to detect and engage hidden cases.

Table 1. JoyAge Collaborative Stepped-Care Service

	Indicated Prevention for Mild Symptoms	Clinical Intervention for Moderate Symptoms	Intensive Clinical Intervention for Moderately Severe Symptoms
Intervention goal	To reduce depressive symptom level to normal level, enhance resilience	To reduce depressive symptom level to mild depression or below	To reduce depressive symptom level to moderate depression or below
Key intervention mode	Psychoeducation on a specific topic (insomnia, pain, stress, and anxiety), or low-intensity psychotherapy	High-intensity psychotherapy	High-intensity psychotherapy
Principal team	DECC	DECC and ICCMW	ICCMW

For older adults with mild depressive symptoms (PHQ-9 score 5-9), 6-8 weeks of indicated prevention with psychoeducation or low-intensity psychotherapy would be provided by the project social workers in the DECC. For participants with moderate symptoms (PHQ-9 score 10-14), 6-8 weeks high-intensity clinical intervention, mainly cognitive behavioral therapy (CBT), would be provided by project social workers from the DECC and ICCMW. For those with moderately severe depressive symptoms, individual CBT or group CBT at higher frequency would be provided by the project social workers from the ICCMW.

Participants should be stepped up to clinical intervention at a more intense level if they showed increased level of depressive symptoms after receiving one rounds of services,

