#### Secondary outcomes

- 1. Lifestyle: Typical Day, a semi-structured interview asking clients about their typical day activities in three domains, physical, social, and mental. A combination of being active in at least two domains would be used as one of the exit criteria.
- 2. Cognition: Hong Kong Montreal Cognitive Assessment 5-Minute Protocol (HK-MoCA 5-Min) (Wong et al., 2015), a validated and reliable cognitive screen for stroke and transient ischemic attack. It includes four items examining attention, verbal learning and memory, executive functions/language, and orientation extracted from the MoCA.
- 3. Support network: asking participants to list out names of people who they would turn to when they feel down, and when they need help for trivial things.
- 4. Perceived environment: Self-developed questions of perceived residential environment derived from sense of community scale (McMillan & Chavis, 1986) and neighbourhood environment walkability scale (Saelens, Sallis, Black, & Chen, 2002).
- 5. Pain management: Using Chronic pain acceptance questionnaire (CPAQ-8) (Fish, McGuire, Hogan, Morrison, & Stewart, 2010), participants will rate the extent to which the eight statements about pain acceptance are true for them on a 7-point Likert scale, and higher scores indicates greater levels of acceptance.

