## Data Analysis

For the main outcome measures of depressive symptoms/risks, wellbeing, and personal recovery, repeated measures analysis and growth curve modeling with three time points will be applied. All results will be reported with the appropriate effect sizes, along with statistical significances and confidence intervals.

To evaluate cost-effectiveness and sustained cost-effectiveness, cost-utility analysis will be used for analyzing data at different time-points. We focus on the quality-adjusted life year (QALY), a generic measure of health, like a currency which combines the quality of life and duration of the quality of life (Luyten, Naci, & Knapp, 2016). It not only captures observable health outcomes but also reflects the subjective appraisals of how bad it is to experience these outcomes from participants' perspective. Findings of cost-utility analysis will be reported as an incremental cost-utility ratio (ICUR),

indicating that the incremental cost per QALYs gained. We will use STATA 14.0 (StataCorp, 2015) for data analysis.

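### T2 is collected only from clients who meet the exit criteria at T1, yet the three-time-point and sustained cost-effectiveness analyses are not restricted to those clients

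*Combined protocol and SAP*

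**What the plan says.** The Design section sets out one group measured at T0, T1 (end of intervention) and T2 (end of exit plan). Assessment Procedures gives T0 and T1 to everyone, with T1 done even after drop-out. After that, "a client is discharged if he/she meets the exit criteria at T1". Only such clients receive the two-month exit plan and the T2 visit, which takes place "for around 30 minutes at T2 for those who are eligible for discharge".

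The full exit criteria are not given. One is named under Secondary outcomes, for the Typical Day interview: "A combination of being active in at least two domains would be used as one of the exit criteria". Table 1 under Interventions lists symptom goals by level, for example "To reduce depressive symptom level to normal level, enhance resilience", but does not call them exit criteria. The same section says: "Participants should be stepped up to clinical intervention at a more intense level if they showed increased level of depressive symptoms". It also refers out people with severe symptoms or raised suicide risk. No T2 is described for either group.

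For the main outcomes, Data Analysis states that "repeated measures analysis and growth curve modeling with three time points will be applied". For the economic part: "To evaluate cost-effectiveness and sustained cost-effectiveness, cost-utility analysis will be used for analyzing data at different time-points". Neither sentence names a population or a way of handling absent T2 data.

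The content of T2 is described in two ways. Assessment Procedures says that it is "specifically on progress in personal goals of recovery". Measurements has all primary outcomes taken at T2, which include PHQ-9, EQ-5D-5L and the service receipt inventory.

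**The concern.** T2 is absent by design for clients who do not meet the exit criteria, and having a T2 depends on status at T1. At least one criterion, activity, is itself a trial outcome. Three natural ways of carrying out the plan would then describe a selected group:

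- a repeated measures analysis of clients with all three visits;
- a T2 mean from discharged clients set against the T0 mean of everyone;
- QALYs after T1 that use T2 EQ-5D-5L.

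If selection is related to symptoms, discharged clients include people whose T1 score was low partly by chance. Their T0–T2 gain can then exceed that of the enrolled population. Their T1–T2 course can drift upward with no real relapse.

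The trial has no control group that would expose either artefact. Its objectives include evidence of effectiveness and cost-effectiveness, and the Background hopes for adoption in regular service. Maintenance among discharged clients could therefore be read as a lasting effect of the programme.

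**Working it through.** **What can be reproduced.** The only relevant figure in the plan is n = 3,000, given without derivation. The plan states no SD, correlation, discharge rate, effect size or PHQ-9 exit threshold. Everything below is therefore illustration on assumed inputs. The exit rules used are not proposals.

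**Step 1: selection in closed form.** Assume that PHQ-9 at T0, T1 and T2 is normal with means 10, 7 and 7, SD 4.5 and equal correlation r. A share q with the lowest T1 scores is discharged. The shift in the discharged T2 mean is −r × SD × φ(z(q))/q.

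With r = 0.6 and q = 0.5 (about 1,500 of 3,000), φ(0)/0.5 = 0.798. The shift is −0.6 × 4.5 × 0.798 = −2.15, so the T2 mean is 4.85 (4.84 by simulation) against a true 7.0.

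- Discharged T2 minus all-participant T0: 4.84 − 10 = −5.16, against a true −3.0.
- T1–T2 in discharged clients: (1 − 0.6) × 4.5 × 0.798 = +1.44, against a true 0.
- T0–T2 within discharged clients: −3.0, which is unbiased here.

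The last line shows that selection at T1 alone need not bias discharged clients' own T0–T2 change. That bias needs a further ingredient, such as the entry range on T0, the scale limits, or an exit rule that refers back to T0.

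**Step 2: add the entry range.** Assumptions: true PHQ-9 mean 6; between-person SD 3.5; within-person SD 2.5; scores rounded and limited to 0–27; entry at T0 of 5–19 (the mild to moderately severe bands in Measurements); the same course after T1 for everyone. True T0–T2 change is −1.82 (2-point effect, half waned), −2.77 (2-point held), −4.56 (4-point held) and −0.84 with no effect.

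| Illustrative exit rule at T1 | Share discharged, 2-point / 4-point | Discharged-only overstatement of T0–T2: 2-point half waned / 2-point held / 4-point held | False T1–T2 worsening: 2-point held / 4-point held |
|---|---|---|---|
| PHQ-9 below 10 | 85% / 94% | 7% / 4% / 1% | +0.45 / +0.21 |
| PHQ-9 below 5 | 38% / 59% | 34% / 20% / 5% | +1.68 / +1.05 |
| Lower PHQ-9 band than at T0 | 57% / 77% | 49% / 31% / 10% | +1.21 / +0.68 |

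Example: lower band, half waned, gives −2.70 against −1.82. The ratio of these rounded values is 1.48, and 49% comes from the unrounded ones. Under the below-10 rule, setting discharged T2 against all-participant T0 gives 33% / 21% / 6%. If clients who miss the first review have one more round and then T2, the half-waned figures fall to 3%, 26% and 34% (same row order).

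**Step 3: likelihood model on all T0 and T1 records.** With exit decided by PHQ-9 alone and the effect half waned, the estimate is −1.81 (below 10), about −1.65 (below 5) and −1.78 (lower band), against −1.82. Most of the selection goes. The below-5 result is 9% too small because the model extrapolates.

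**Step 4: the one stated criterion.** Suppose that exit depends only on activity in two or more domains (60% of clients, assumed). If activity is unrelated to later course, overstatement is 0%. Now suppose that activity correlates 0.7 with a factor that shifts T2 by 0.5 or 1 point per SD. Overstatement is then 12% or 24% (half waned) and 4% or 8% (4-point held). In the half-waned case a likelihood model without the domain count gives the same 12% or 24%.

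**Step 5: economics.** T2 EQ-5D-5L and the T2 service inventory exist only for discharged clients. Costs from authority records could cover everyone. Unless one population is fixed, the numerator and denominator of a T2-based ratio can refer to different people.

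**The case against.** The plan does not say that it will use complete cases, nor that it will compare discharged T2 with everyone's T0. It names growth curve modelling, which can use every T0 and T1 record and which Step 3 shows to be nearly sufficient if exit depends on PHQ-9. This stands. A reader might infer that the planned models are invalid, and the documents do not support that. What remains is that repeated measures analysis is also named with nothing to stop a complete-case version, and that the one stated exit criterion lies outside a PHQ-9 model.

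A reader might also infer that exit depends on a PHQ-9 threshold and that the bias is therefore near 49%. The documents state no such threshold, and Table 1 gives treatment goals, not exit rules. The larger percentages belong to constructed rules and a small, waning effect. With a 4-point effect held, the range is 1% to 10%.

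It can fairly be said that a post-exit-plan visit does not exist for people given no exit plan, so the main gap is an undefined target population. That is right, and it makes labelling T2 results as conditional on discharge a central part of the remedy.

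The cost-utility sentence does not name T2. Its use of T2 is inferred from the word sustained, the plural time-points and the presence of EQ-5D-5L among the primary outcomes taken at T2.

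Finally, the two descriptions of T2 may be emphasis and not conflict, since recovery goals are themselves primary outcomes. If T2 did cover goals alone, the PHQ-9 and QALY issues would fall away. So, however, would any three-time-point depression model.

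**Conclusion.** The point holds as a gap between who has T2 and what the analysis claims from it. T2 covers clients who meet the exit criteria at T1, and the three-time-point and sustained cost-effectiveness analyses are not restricted to them. This should be fixed.

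The size is not derivable from the documents. On the PHQ-9 inputs and exit rules assumed above, it ranges from negligible to about half of the true change. A 0% result is possible under the only criterion actually stated. T0–T1 change in all participants is free of this selection. It is not free of regression to the mean from entry, about −0.84 PHQ-9 points with no effect on the same assumptions. Confidence is medium, because the full exit criteria and the form of the repeated measures analysis are unknown.

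**What to change.** 1. In Data Analysis, make T0–T1 change in all participants the main effectiveness result. Fit the three-time-point analysis as a likelihood mixed or growth curve model to all enrolled participants' T0, T1 and available T2 records, not to complete cases.
2. Report observed T2 means, T1–T2 change and T2-based QALY or cost-utility results as maintenance among discharged clients, with the number and share discharged, and not as a sustained programme effect. Use the same population for costs and QALYs in any T2-based ratio.
3. As a sensitivity analysis only, add T1 exit-criterion variables such as the Typical Day domain count as auxiliary variables. State that the all-participant T2 estimate is hypothetical for people given no exit plan, and that it extrapolates where a criterion is strictly required. An analysis returning non-discharged clients to their T0 level may be shown as a pessimistic scenario. It is not a bound, because clients who worsened may end above T0.
4. Reconcile Assessment Procedures with Measurements on what T2 measures. Reconcile Assessment Procedures with Interventions on whether clients discharged after a later round contribute T2.

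The cost is modest extra analysis and wording, with no new participants or visits. The T2 figure will probably be less favourable than the discharged-only one. In the half-waned, lower-band illustration it is −1.78 instead of −2.70.
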